8.3 ADDITIONAL SUB GROUP ANALYSIS

The primary and secondary endpoint will be analyzed based on age, sex, race/ethnicity or other variable such as subjects behavior (smoking, diet, handedness, exercise, etc..)

8.4 SAMPLE SIZE

N/A – Pilot Study

8.5 MEASURES TO MINIMIZE BIAS

ENROLLMENT/ RANDOMIZATION/ MASKING PROCEDURES

In order to avoid bias, the subjects will be randomized to receive treatment on either their left or right arm. All evaluators of pictures will be blinded as to which technique was used on which side. In order to avoid bias, the evaluator will not be the primary investigator.

To ensure only the clinical investigator performing the procedures and the study coordinator know

the assignment of arms, each subject will have an envelope assigned to them to be held by the study coordinator with the subject's name on the outside and the assignment on the inside. Only during treatments does the study coordinator allow the clinical investigator to see the inside of the envelope.

The skin biopsy samples will be coded to ensure blinded analysis.

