I agree to ensure that all staff members involved in the conduct of this study are informed about their obligations in meeting the above commitments.

Principal Investigator: [name]

_Date: ______ Signature

Title:

A Prospective, Randomized, Split-Arm Clinical Study Investigating the Efficacy and Safety of Sciton's Broad Band for the Treatment and Prevention of Senile Purpura

Précis:

There will be ten subjects, 5 older subjects over 65 years of age with at least one ecchymotic lesion on each arm measuring at least one cm, and 5 subjects under 35 years of age. All subjects will be randomized to undergo 4 Sciton Broad Band Light (BBL) treatments on either their left or right arm one week apart. Subjects will fill out questionnaires, have pictures of their lower arms taken, and will be graded and measured by evaluators regarding the number and size of their ecchymoses as well as side effects such as blistering, pain, erythema, and swelling. One day after their 4th treatment, subjects will have biopsies done to be analyzed for changes in histology and gene expression. The subjects will follow up at 30 days after their last treatments for final pictures of their lower arms and evaluations.

Objectives:

Primary Objectives: To assess the efficacy of BBL in improving the appearance of senile purpura

Important Secondary Objectives:

- 1. To assess the safety of a new BBL protocol for treating and preventing senile purpura
- 2. To assess the efficacy of BBL in reducing skin tears
- 3. To assess the efficacy of BBL to improve the histology of the skin
- 4. To assess the efficacy of BBL to increase epidermal thickness
- 5. To assess the efficacy of BBL to change gene expression

Endpoint

Primary Endpoints:

- Mean absolute difference in the BBL treated arms as compared to the non-treated arms of those with senile purpura in the total square area of purpuric lesions from the first treatment to 30 days after the last treatment
- Mean absolute difference in the BBL treated arms as compared to the non-treated arms of those with senile purpura in the number of purpuric lesions from the first treatment to 30 days after the last treatment

Important Secondary Endpoints:

1. Measurement of pain, swelling, blistering, erythema, and all sideeffects immediately after each procedure, as well as 24 hours, 48 hours, and 7 days after the procedure.

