2.3 POTENTIAL RISKS AND BENEFITS

2.3.1 KNOWN POTENTIAL RISKS

Common potential risks of BBL include swelling, pain, scabbing, blistering, reduction of hair and lentigenes, erythema, pruritus, lightening and darkening of the skin, and reactivation of herpes infection. Rare but potential risks of BBL include severe burn, skin ulceration, scarring and infection.

Common potential risks of a skin biopsy include bleeding and scarring while rare but potential risks include infection and allergy to the lidocaine, bandages, or sutures used in the procedure.

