3 STUDY DESIGN, OBJECTIVES, AND ENDPOINTS

3.1 DESCRIPTION OF THE STUDY DESIGN

- A Prospective, Randomized, Split-Arm Clinical Study
- Single Center
- Study agent: Sciton's BBL
- Study Interventions: BBL Treatment on Day 0, Day 7, and Day 21
- Evaluations on Day 0, Day 7, Day 14, Day 21, Day 22, Day 51.

This will be a prospective, split-arm clinical study in which 5 subjects will be randomized to which arm will be treated with Sciton's BBL.

All subjects will have their arms shaved prior to the procedure and cleaned thoroughly with alcohol. After the procedure a zinc-based sunscreen will be applied to both arms.

Before each of the four treatments and 30 days after the last treatment, the subjects' number and square area of ecchymoses will be measured by an evaluator. Side effects will be measured on Day 0, 1, 2, 7, 14, 21, 22 and 51. Digital photography of subject's arms will be done on day 0, 7, 14, 21, and 51.

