3.2.2 PRIMARY ENDPOINT

➤ Primary Endpoint: Mean absolute difference between the treated and non-treated arms in the change of total square area and number of ecchymoses from baseline to 30 days after the last treatment.

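### Section 8.5 intends that the lesion evaluator not know the treated side, but no stated procedure maintains that masking, and Section 6.3 allows data to be disregarded without criteria or blinding

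*Combined protocol and SAP*

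**What the plan says.** **Primary data.** Section 3.2.2 defines the endpoint as "Mean absolute difference between the treated and non-treated arms in the change of total square area and number of ecchymoses", comparing Day 51 with Day 0. Section 3.1 says that before each treatment and at 30 days the "number and square area of ecchymoses will be measured by an evaluator". Sections 6.2.2, 6.2.3 and 6.2.5 place this measurement at the visits, and the schedule in 6.2.8 lists photographs and evaluator measurements as separate rows.

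**Masking.** Section 8.5 uses a coordinator-held envelope. Its purpose is given as "To ensure only the clinical investigator performing the procedures and the study coordinator know" the assignment, and "Only during treatments does the study coordinator allow the clinical investigator to see the inside of the envelope". The evaluator is not to be the primary investigator. Explicit blinding of those who supply outcome data is stated for picture evaluators ("All evaluators of pictures will be blinded as to which technique was used on which side") and, by coding, for biopsy samples.

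**Side effects.** The Précis has subjects "graded and measured by evaluators regarding the number and size of their ecchymoses as well as side effects such as blistering", among other reactions. Sections 6.2.2, 6.2.3 and 6.2.5 record adverse events through the participant and the investigator. Section 2.3.1 lists as common risks "blistering, reduction of hair and lentigenes, erythema, pruritus, lightening and darkening of the skin".

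**Arm preparation.** Section 3.1 says "All subjects will have their arms shaved prior to the procedure and cleaned thoroughly with alcohol". Sections 6.2.2, 6.2.3 and 6.2.5 also shave the lower arms or both lower arms. Section 6.1.1 shaves the assigned arm.

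**Disregarding data.** Under Section 6.3, if a subject changes medication or has a treatment or procedure, the primary investigator decides whether to terminate participation early or leave certain data out of the final analysis.

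**The concern.** Lesion count and outline involve judgement, and each subject is their own control, so the primary contrast depends on the evaluator treating the two arms alike. An envelope hides a record. It does not hide skin, hair growth or what a subject says, and no sham on the untreated arm is described. An evaluator who learns the side could lean, without meaning to, in the same direction in every subject, and the paired test would count that lean as effect.

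Only the 5 older subjects in the Précis have senile purpura, so leaving out one of them removes 1/5 = 20% of the primary data. If that choice can be made knowing the side or the outcome, it is a second way to shift the result.

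**Working it through.** **Step 1. Order of events at each visit.**

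| Visit | Order as listed | Consequence |
|---|---|---|
| Day 0 (6.2.2) | Shave, photograph, measure, treat | If only the assigned arm is shaved (6.1.1), the side shows in the baseline photographs and measurement |
| Days 7, 14, 21 (6.2.3) | Adverse events, questionnaire with evaluator review, measure, shave both arms, photograph, treat | Subject-reported information precedes measurement; regrown hair is still present when lesions are measured |
| Day 51 (6.2.5) | Adverse events, questionnaire with evaluator review, measure, shave both arms, photograph | The same, at the primary time point |

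Baseline is therefore protected only if both arms are shaved. Sunscreen on both arms (3.1) comes after the procedure and the biopsies on both arms come at Day 22, so neither protects Day 0.

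**Step 2. Where the blinded picture reading goes.** No primary, secondary or exploratory endpoint (Précis; 3.2.2 to 3.2.4) is clearly assigned to a picture reading. Section 8.5 does not say whether the picture evaluators are the same people as the visit evaluator, and the Précis mentions pictures and evaluators in one sentence. This is an ambiguity.

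**Step 3. Section 6.3.** A trigger is given. What may be disregarded, by what rule, when, and blind to what are not given. The documents do not say whether the primary investigator is the treating investigator who sees the envelope.

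**Step 4. Sensitivity, for illustration only.** The plan has no figure to reproduce: Section 8.4 gives no sample size calculation, and no SD, alpha or evaluator lean is stated. From the documents: 5 purpura subjects, a paired t-test, an alternative written as greater than zero (8.1). Assumed: normal paired differences, no true effect, alpha as shown.

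*(a) Constant lean of b SDs of the paired difference.* The statistic is noncentral t with 4 degrees of freedom and noncentrality b × √5. For b = 0.25 this is 0.25 × 2.236 = 0.559; for b = 0.5 it is 1.118. The one-sided 5% critical value is 2.132.

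| Lean | One-sided 5% | One-sided 2.5% | Two-sided 5% |
|---|---|---|---|
| 0.25 SD | 12.0% | 6.4% | 7.2% |
| 0.5 SD | 23.9% | 13.8% | 14.1% |

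A lean of 0.193 SD doubles a one-sided 5% error to 10%. In lesions, a lean of one per subject is 0.25 SD if the SD is 4 and 0.5 SD if it is 2 (1/4 and 1/2).

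*(b) Outcome-aware dropping.* Simulated null data; reject if significant with all 5, or with 4 after dropping one fixed subject who meets a 6.3 trigger. The error is about 7.1% (one-sided 5%), 3.7% (one-sided 2.5%) and 7.5% (two-sided 5%). Freely dropping any one of the five would give 15.4% at one-sided 5%, but 6.3 does not allow that without a trigger.

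**The case against.** **Masking is intended.** A reader might infer that the visit evaluator is unmasked by design. The documents do not support that: 8.5 limits knowledge of the side to two people, which excludes the evaluator, and the envelope is in use throughout the treatments. What stands is narrower: nothing visible says how that intent is kept up at later visits.

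**Subject instructions are only partly visible.** It is tempting to say that subjects are never asked to withhold the side. The consent pages, questionnaires and written instructions are not in the text reviewed, so one can say only that the visible text is silent. What the evaluator would learn from the adherence questionnaire is likewise unknown.

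**Side-effect grading by evaluators rests on one summary sentence.** The detailed sections use subject questionnaires and the investigator. This is a conflict to reconcile, not proof that the same person does both.

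**Picture reading.** A reader might conclude that it serves no endpoint at all. Sections 3.1 and 6.2.8 favour separate activities, but the Précis and 8.5 leave room for the other reading.

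**This is a pilot.** That limits the weight of error rates, and the lean and dropping models assume behaviour that is always favourable. Both points are fair. The plan nevertheless tests efficacy formally in 8.1, and the remedy is cheap.

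**Conclusion.** The point holds as a gap in procedure. The person who supplies the primary data is meant to be masked, but the visible text gives no step that keeps this so; it places side-revealing information before the measurement and contradicts itself on which arm is shaved. Section 6.3 separately leaves the exclusion of data open. Bias is plausible and has not been shown, and its size is unknown. The figures of 12% to 24% for a lean and about 7% for one optional exclusion rest on 5 subjects, no true effect, normal differences, one-sided 5% and an assumed lean or outcome-aware choice. They show how sensitive so small a comparison is; they do not predict what will happen. This is a change the plan should make, with medium confidence: the omission is clear, its effect is not.

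**What to change.** 1. **Section 8.5.** State that the visit evaluator is masked to side, that subjects are asked not to disclose it, and that lesions are measured before adverse-event recording, side-effect grading or questionnaire review. Reconcile the Précis with 6.2.2, 6.2.3 and 6.2.5 on who grades side effects.
2. **Shaving.** Reconcile 6.1.1 with 3.1, 6.2.2, 6.2.3 and 6.2.5 so that both arms are prepared identically before photographs and measurement.
3. **Supportive check.** Keep live measurement primary. Prespecify a reading of lesion number, and of area if a scale is in view, from the Day 0 and Day 51 photographs by the blinded picture evaluators already planned, with images coded for subject, side and visit. State whether these readers are the visit evaluator; no added reader is required.
4. **Section 6.3, analysis data only.** Exclude data only by criteria written in advance and applied blind to side and outcome, and always report the analysis of all available data from randomised purpura subjects.

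**Cost.** Protocol wording, a scale in the photographs if area is to be read, and about 5 subjects × 2 arms × 2 visits = 20 readings. Area on a curved forearm is less exact in a photograph, and hair or pigment cues may remain. With 5 subjects the check cannot separate evaluator lean from measurement error, so it supports the live result and does not replace it.

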2.1 BACKGROUND INFORMATION

Senile Purpura is a benign common condition characterized by recurrent formation of ecchymosis on the extensor surfaces of forearms and hands following minor trauma. Other names of this condition are Bateman purpura, named after British dermatologist Thomas Bateman, who first described it in 1818, and actinic purpura, because of its association with sun damage (1).

More recently in 2007, Kaya and Saurat coined the term dermatoporosis to describe the chronic cutaneous fragility of aging skin. Dermatoporosis features include thinning atrophic skin, purpura, skin lacerations and delayed healing (2).

This condition affects over 10% of those aged over 65 years old and is equally common in males and females. Risk factors are known to include the use of oral or topical corticosteroids and anti-coagulants (3).

With age and sun damage, the dermis becomes thin. As a result, this condition results from superficial vessels tearing even with negligible trauma. The subsequent extravasation of blood into the surrounding dermis results in the development of ecchymosis. Histologically, the epidermis is thinned and the dermis demonstrates significantly reduced amounts of collagen replaced by abnormal elastic fibers, as well as extravasated red blood cells (4).

Intense pulsed light (IPL) is non-coherent, non-collimated, polychromatic light energy. IPL emits different wavelengths that target specific chromophores. This makes IPL a versatile therapy with many applications, from the treatment of pigmented or vascular lesions to hair removal and skin rejuvenation. Its large spot size ensures a high skin coverage rate and ease of use over large areas. The treatment has very little downtime given its non-ablative nature which makes it an attractive option. In many cases, IPL is similar to laser therapy in effectiveness, convenience, and safety and together with its versatility will lead to an expanded range of applications and possibilities in the future.

Relevant Clinical Research

Published studies on treatments for senile or actinic purpura or dermatoporosis are very limited. In one small double blinded study (N=14) published in 1995 in The Archives of Dermatology, they showed twice daily treatment with retinoic acid cream resulted in significant reduction in Bateman's actinic purpura after two weeks, however there were no significant differences after that time (6).

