6 STUDY PROCEDURES AND SCHEDULE

6.1 STUDY PROCEDURES/EVALUATIONS

6.1.1 STUDY SPECIFIC PROCEDURES

- Medical history obtained and verbally verified
- Assigned arm meeting inclusion criteria is shaved to remove all hair
- Digital Pictures taken of bilateral hands and arms
- Counseling the subjects on the treatment that they will be receiving and post-care instructions.
- The study coordinator will check before the patient leaves that all appropriate photos and paperwork have been completed.
- BBL study treatment will be done according the protocol below outlining specific settings

BBL Only Protocol

1st Treatment Settings

- 1. SkinTyte Filter ST: 150 Joules, 15msec, 15 degrees for 10 continuous passes in alternating directions (5 each direction)
- 2. 590 Filter: 8J, 15msec, 15 degrees x 2 passes
- 3. 590 Filter: 10J 15msec, 15 degrees x 2 passes
- 4. 560 Filter: 8J, 15msec, 15 degrees x 2 passes

2nd Treatment Settings

If any answers on the post procedure side effects questionnaire from day 0,1, or 2 were SEVERE or if the patient had blisters from the previous treatment

Decrease Step 3 & 4 by 2 Joules

1. SkinTyte Filter ST: 150 Joules, 15msec, 15 degrees for 10 continuous passes in alternating directions

- 2. 590 Filter: 8J, 15msec, 15 degrees x 2 passes
- 3. 590 Filter: 8J 15msec, 15 degrees x 2 passes
- 4. 560 Filter: 6J, 15msec, 15 degrees x 2 passes

If any answers on the post procedure side effects questionnaire on day 0,1, or 2 were MODERATE with NO blistering

Decrease Step 3 & 4 by 1 Joule

- 1. SkinTyte Filter ST: 150 Joules, 15msec, 15 degrees for 10 continuous passes in alternating directions
- 2. 590 Filter: 8J, 15msec, 15 degrees x 2 passes
- 3. 590 Filter: 9J 15msec, 15 degrees x 2 passes
- 4. 560 Filter: 7J, 15msec, 15 degrees x 2 passes

If all answers on the post procedure side effects questionnaire on day 0,1, or 2 protocol were MINIMAL

Keep Settings the same as previous visit

- 1. SkinTyte Filter ST: 150 Joules, 15msec, 15 degrees for 10 continuous passes in alternating directions (5 each direction)
- 2. 590 Filter: 8J, 15msec, 15 degrees x 2 passes
- 3. 590 Filter: 10J 15msec, 15 degrees x 2 passes
- 4. 560 Filter: 8J, 15msec, 15 degrees x 2 passes

If all answers on the post procedure side effects questionnaire on day 0,1, or 2 protocol were NONE

Increase Step 1 by 10 additional passes and Increase Step 3 & 4 by 1 Joule

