6.2.2 ENROLLMENT/BASELINE

Enrollment/Baseline Visit (Visit 1, Day 0) Treatment #1

- Review in depth the study design with subjects and obtain informed consent of potential participants verified by signature
- Perform examination and verbally review subject's medications, medical history, and subject questionnaire to determine eligibility based on inclusion/exclusion criteria

- Obtain demographic information
- Shave the hair on the subjects' lower arms
- Take digital pictures of subjects' lower arms
- Have evaluator measure the size and number of bruises and skin tears
- Perform the BBL treatment on assigned arm per protocol
- Record adverse events as reported by participant or observed by investigator
- Perform protocol adherence check by study coordinator
- Expected post-procedure side effects and possible emergent situations reviewed with subjects and post-op written instructions given

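### Subjects know which arm gets BBL, contrary to the wording of Section 8.5, and no equal home care of the two arms is specified, so the between-arm contrast could be biased either way by an unknown amount

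*Combined protocol and SAP*

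**What the plan says.** Section 8.5 randomises the treated side and keeps each assignment in an envelope held by the coordinator. The stated aim is "To ensure only the clinical investigator performing the procedures and the study coordinator know" the assignment. The same section says "All evaluators of pictures will be blinded as to which technique was used on which side" and that biopsy samples are coded. It says nothing about masking the subject.

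The visit schedule has staff "Perform the BBL treatment on assigned arm per protocol" (Section 6.2.2), and the Précis gives four such treatments. No sham on the other arm is described. Section 6.1.1 lists "Counseling the subjects on the treatment that they will be receiving and post-care instructions", and the baseline visit ends with "possible emergent situations reviewed with subjects and post-op written instructions given"; the later treatment visits review those instructions. The content of the instruction sheet is not in the documents.

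Section 2.1 describes the condition as "recurrent formation of ecchymosis on the extensor surfaces of forearms and hands following minor trauma". The primary endpoint (Section 3.2.2) compares the two arms on the change in number and total area of ecchymoses from baseline to 30 days after the last treatment, which is Day 51.

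On symmetry between arms, Section 3.1 says "After the procedure a zinc-based sunscreen will be applied to both arms", and Section 6.2.3 has both lower arms shaved at each later treatment visit.

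**The concern.** The untreated arm of the same person is the control, so anything the subject does differently to the two arms after treatment starts goes straight into the primary contrast. A subject who knows the treated side might guard or cover that arm, which would look like a BBL benefit. Equally, a subject might relax care of it because it has been treated, or put more effort into the other arm, which would hide a benefit.

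A blinded evaluator does not help, because the lesions counted would be real and only their cause would be misattributed. Randomising the side balances handedness on average, but it does not prevent behaviour that changes once the subject knows the side.

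**Working it through.** The plan gives no figure to reproduce: Section 8.4 has no sample size calculation, and no effect size, standard deviation or alpha is stated. The check is mainly a reading of the text, followed by two illustrations of size.

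**1. Does the subject know the side?** No section says so outright; it is inferred. BBL is applied to one arm for about 15 minutes per session (Section 5.1.2, duration of therapy). The subject is counselled on the treatment and completes side-effect questionnaires at home on Days 1 and 2 (study schematic). Section 2.3.1 lists pain, erythema and blistering among the common risks. With no sham, no other reading is plausible, so the word *only* in Section 8.5 is untrue for subjects.

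**2. Can behaviour reach the endpoint?** Yes, in part. Section 2.1 makes trauma the trigger, and protection and arm use can alter trauma. The same section says that vessels tear even when the trauma is negligible, so a subject can influence the trigger but not fully control it.

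**3. What is equalised between arms?**
- In the clinic: sunscreen on both arms and bilateral shaving at later visits.
- At home: no section asks for equal protection or product use. Section 6.3 restricts changes in anticoagulants and prednisone, and bars procedures on the treatment arm. Section 2.2 lists several topical products as current treatments. Recent topical retinol is an entry exclusion (Section 4.2); for the other topicals, no rule on one-sided use is given.
- In the data: Section 3.2.4 names dominant hand and time in the sun, and Section 8.3 names handedness and exercise among the subgroup variables. None of these is a record, by arm, of protection, products or knocks.

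**4. Size in lesions.** Assume that home behaviour changes new lesions on one arm by a proportion p of 10% to 30%, that lesion count moves in proportion, and that BBL has no effect. Then shift = p × L, where L is lesions per arm.

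| L per arm | Source | p = 10% | p = 30% |
|---|---|---|---|
| 1 | entry minimum per arm in the Précis | 0.10 × 1 = 0.1 | 0.30 × 1 = 0.3 |
| 3 | assumption | 0.10 × 3 = 0.3 | 0.30 × 3 = 0.9 |
| 7.5 | 15 ÷ 2, if the cited 15 covers both arms | 0.10 × 7.5 = 0.75 | 0.30 × 7.5 = 2.25 |
| 15 | Section 2.1, mean in a cited 6-subject study, if per arm | 0.10 × 15 = 1.5 | 0.30 × 15 = 4.5 |

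The range p is an assumption with no source in the documents. Area, the other primary measure, cannot be illustrated in the same way because the documents give no typical area.

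**5. Effect on the test.** Inputs: a one-sided paired t-test (Section 8.1), with benefit taken as the positive direction; n = 5 subjects with purpura (Précis); alpha assumed to be 0.025 or 0.05; bias and true effect in SD units of the within-subject difference, both assumed. The rejection rate comes from the noncentral t distribution with n − 1 = 4 degrees of freedom and noncentrality (effect + bias) × √n.

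| Effect, bias (SD) | Noncentrality | alpha 0.025 | alpha 0.05 |
|---|---|---|---|
| 0, 0 | 0 | 2.5% | 5.0% |
| 0, +0.25 | 0.25 × √5 = 0.56 | 6.4% | 12.0% |
| 0, +0.5 | 0.5 × √5 = 1.12 | 13.8% | 23.9% |
| 1, 0 | 1 × √5 = 2.24 | 40.1% | 58.0% |
| 1, −0.5 | 0.5 × √5 = 1.12 | 13.8% | 23.9% |

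A bias of either sign therefore matters even at this sample size, but a false positive is far from assured.

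**The case against.** The strongest reply is that Section 8.5 never claims to blind subjects. It names the picture evaluators and the coded biopsies, and the envelope is a device to keep the assignment from other staff. Correcting one loose word alters no procedure. Known side is inherent in a split-arm pilot without a sham, and side randomisation and clinic sunscreen are already in place. This is fair as to intent. It does not supply the missing request for equal care at home, which is the part that could affect the result.

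Several stronger readings are tempting, and the documents do not support them:
- *Nothing records home care by arm.* This cannot be established. The subject, adherence and side-effect questionnaires and the instruction sheet are not reproduced and may already cover both arms. The most that can be said is that no such item or instruction appears in the documents.
- *The subject controls the cause of the lesions.* Section 2.1 does not go that far. Moreover, each subject with purpura enters with a lesion on each arm, so part of the change to Day 51 is the fate of existing lesions, which guarding against new trauma does not affect.
- *One-sided sun protection over 51 days would change lesion counts.* Section 2.1 presents sun damage as a cause of dermal thinning and trauma as the trigger. It gives no basis for an effect over that period.
- *The bias is 1.5 to 4.5 lesions.* That needs 15 lesions per arm. The cited mean is not stated to be per arm, and entry here needs only one lesion on each arm.

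It is also true that a left/right recall item from unmasked subjects can itself be biased, and that five subjects with purpura cannot support an adjustment.

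**Conclusion.** The concern stands in limited form. The masking sentence in Section 8.5 is wrong for subjects, and the documents specify symmetry between arms only in the clinic. Unequal protection or product use at home could therefore bias the primary contrast despite blinded evaluation. The direction is not known, and neither is the size: 0.1 to 0.9 lesions at 1 to 3 per arm, rising to 1.5 to 4.5 at 15 per arm, all resting on the assumed 10% to 30% change and on proportionality.

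A reader might infer that any positive result would be an artefact, or that all aftercare ought to be duplicated on the untreated arm. Neither follows. No net bias has been shown, and medical aftercare of treated skin is a clinical matter on which this point takes no position. The change is worth making because it is cheap and because neither evaluator blinding nor randomisation of side does the same job.

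**What to change.** 1. Correct Section 8.5 to say that subjects are not masked to the treated side, and list this as a limitation.
2. Instruct subjects to protect and handle both arms alike, and to use the same sun protection, coverings and non-prescribed products on both, through Day 51. Leave medical aftercare of treated skin as the investigator sets it.
3. Check the adherence questionnaire already completed at Days 7, 14, 21 and 51. Unless it already has one, add a left/right item on protection, products and notable knocks. Report it descriptively by arm beside the primary result, and do not use it for adjustment.

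The cost is one corrected sentence, one instruction and at most one questionnaire item, with no change to treatment, visits or sample size. The downsides are a slight extra burden on subjects and an item whose answers may be coloured by knowing the treated side.
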